13.8.	Appendix H. Contraception Guidance.....	121
13.9.	Appendix I. EQ-5D-3L (English) Questionnaire v1.1	123
13.10.	Appendix J. EQ-5DK3L (Spanish) Questionnaire v1.1	126
13.11.	Appendix K. EQ-5DK3L (Simplified Chinese) Questionnaire v1.1.....	129
13.12.	Appendix L. EQ-5DK3L (Vietnamese) Questionnaire v1.1.....	132

PROTOCOL SYNOPSIS

Study Title	Phase 2 study of Cryoablation Plus Nirogacestat for Desmoid Tumor
Study Drug and Procedure	Nirogacestat (Ogsiveo™) in combination with cryoablation
Study Description	Single-center, single arm study
Study Phase	Phase 2
Study Purpose	Treatment
Primary Objective	To assess the effects of combination therapy with cryoablation plus nirogacestat on efficacy by evaluation of the clinical benefit rate (CBR = CR + PR + SD) at 1 year in subjects with progressive or symptomatic desmoid tumor. Response will be assessed according to Response Evaluation Criteria in Solid Tumors (RECIST v1.1).
Primary Endpoint	Clinical benefit rate (CR + PR + SD) at 1 year from treatment start with nirogacestat. Response will be assessed according to RECIST v1.1.
Secondary Objective(s)	
 1. To assess the effects of combination therapy with cryoablation plus nirogacestat on efficacy by evaluation of the clinical benefit rate (CBR) at 1 year in subjects with progressive or symptomatic desmoid tumor. Response will be assessed according to the modified RECIST criteria (mRECIST). 2. To assess the effects of combination therapy with cryoablation plus nirogacestat on efficacy by evaluation of median disease progression. 3. To assess the effects of cryoablation plus nirogacestat on tumor response (as defined by objective response rate) at 1 year 4. To assess the time to response from the start of treatment with nirogacestat to the first objective tumor response 5. To assess the duration of response from time of response to time of progression 6. To assess safety and tolerability of cryoablation plus nirogacestat in subjects with progressive or symptomatic desmoid tumors
Exploratory Objective	
 • To evaluate effects of cryoablation plus nirogacestat on quality of life. • To correlate changes during treatment with response using the Nanostring CosMX SMI on biopsy samples.

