Secondary Endpoints	
 1. Clinical benefit rate (CR + PR + SD) at 1 year from treatment start with nirogacestat. Response will be assessed according to mRECIST. 2. Median progression free survival will be determined radiographically using RECIST v1.1, mRECIST and volumetrically (change in tumor volume as assessed by MRI volumetric). 3. Objective response rate at 1 year (RECIST v1.1, mRECIST and MRI volumetric); the percentage of subjects who start study treatment and achieve an objective response (CR or PR), will be calculated. 4. Time to response (RECIST v1.1, mRECIST and MRI volumetric) 5. Duration of response (RECIST v1.1, mRECIST and MRI volumetric) 6. AEs will be tabulated with frequencies and percentages for grade, severity, status, and relationship to study drug or study procedure. Assessment will be from time of consent until 30 days after the last treatment.
Exploratory Endpoint	
 • Changes from baseline in patient-reported outcomes (EQ-5D-3L)
Indication	Desmoid tumor
Sample Size	Up to 23 enrolled subjects, to achieve 20 evaluable subjects
Eligibility Criteria	Due to length, the Eligibility Criteria are only presented in one instance. Eligible subjects will be subjects \geq 18 years of age with progressive or symptomatic desmoid tumor that is at least 50% but less than 75% treatable with cryoablation. See Section 3, Subject Selection.
Dose	Nirogacestat 150 mg po BID (150 mg twice-daily) One cycle of treatment = 28 days.
Treatment and Procedural Summary	
 1. Nirogacestat 150 mg by mouth twice-daily continuously for Cycles 1 through 3. 2. Cryoablation procedure (single session) of one tumor mass between Cycles 3 and 4 of nirogacestat treatment. 3. Continued treatment with nirogacestat for Cycles 4 through 26. Treatment with nirogacestat may continue via this study protocol for up to 24 months (26 cycles of treatment), unless there is progression of disease, intolerance, start of new anticancer therapy (as defined in Sections 5.7.2 and 5.7.3), or one of the criteria in Section 3.7 (Subject Study Completion or Termination) occurs. 4. After 24 months of treatment, if clinically indicated, a subject may transition to commercial nirogacestat supply, once the subject has completed the End of Treatment (EOT) visit and is off study.

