1.1. Study Rationale

In this trial, we propose the combination of systemic therapy with nirogacestat and cryoablation to maximize the benefits of both modalities for subjects with growing or symptomatic desmoid tumors. It is hypothesized that the combination will provide long-lasting disease control and a quick time to treatment response.

This phase 2 study will enroll participants \geq 18 years of age. The pharmacokinetics (PK) and optimal dosing of nirogacestat in younger participants has not been established.

Treatment will consist of a 3-month lead-in period of nirogacestat, followed by cryoablation procedure (single treatment), followed by continued nirogacestat treatment for up to a total of 24 months (maximum 26 cycles of treatment), unless disease progression or one of the criteria in Section 3.7 (Subject Study Completion or Termination) occurs. The lead-in period will allow assessment of the response to nirogacestat-alone and potentially lead to improved cryoablation success if there is tumor shrinkage.

In order to assess increased efficacy of combination therapy over single-modality cryoablation, results will be compared to historical data from the Stanford existing cryoablation population treated at Stanford. For these subjects, two-thirds are unable to be completely ablated and most of those patients will have clearly recurrent disease at 6 months. Therefore, we hypothesize that adding on nirogacestat to cryoablation will lead to an 80% clinical benefit rate at 1 year.

Nirogacestat alone has a RECIST response of 29% of patients at a median of 24 months.¹ At 1 year, the ORR was 2 of 17 (12%).

To evaluate effects of cryoablation plus nirogacestat on quality of life (QOL), we will collect patient-reported outcome (PRO) measures using the EQ-5D-3L.

To remain consistent with prior inclusion criteria for desmoid trials, we will only include subjects with growing or symptomatic desmoid tumors. In addition, we will standardize the cryoablation procedure by limiting subjects to 1 cryoablation treatment session at time of intervention and desmoid tumors that can be at least 50% treated with cryoablation but are $<$ 75% cryoablitable.

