3.5.1. Definition of On-study

For the purposes of this study, the “on-study” date for each subject will be considered to be the date that subject receives first interventional treatment. This date may be used as the cut-off criteria for which subjects will or will not be included in results reported to ClinicalTrials.gov.

Note that for the purposes of OnCore subject registration and Stanford IRB Unanticipated Problem reporting, subjects are considered to be study participants when consented.

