4.2. Other Procedures: Cryoablation

Cryoablation of the tumor will occur between investigational agent treatment Cycles 3 and 4, and will be performed according to standard procedures. The cryotherapy device will be an FDA-approved cryoablation system used according to its approved labeling within the Stanford University Medical Center.

Prior to the cryoablation procedure, the interventional radiologist will review cross-sectional imaging studies to formulate a treatment plan, including identifying the target lesion appropriate for treatment, the number and type of cryoablation probes needed, and the optimal percutaneous access approach. Subjects will be limited to one cryoablation treatment session at time of intervention for desmoid tumors that can be at least 50% treated with cryoablation but are < 75% cryoablutable; the cryoablation will be subtotal. For lesions that are in close proximity to freeze-sensitive tissues, such as bowel or skin, the cryoablation treatment will be performed with a safe distance (≥ 5 mm) between the edge of the tissue to be frozen (the "iceball") and the freeze-sensitive tissue.

The cryoablation procedure will be performed with general anesthesia in an MR procedure room. Limited MRI will be obtained, and the desired access site(s) will be marked on the subject's skin. After sterile preparation of the treatment field and application of local anesthesia, cryoablation probes will be sequentially placed percutaneously into the target lesion using MRI and/or ultrasound guidance. After all cryoablation probes are positioned appropriately, cryoablation will be performed with 1 or more freeze-thaw cycles. Iceball growth will be monitored by MRI. After active thawing, the probes will then be removed and sterile dressings applied. Immediate post-treatment MRI without and with contrast will be obtained.

Cryoablation of the tumor will be performed using standard technique. In brief, a total of 15-30 minutes of freezing time will be administered to the tumor in two or three freeze cycles, separated by 10-30 minutes of active and/or passive thawing using the Visual-ICE Cryoablation System. Care will be taken to avoid off-target ablation of sensitive structures such as bowel and

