10.2. Study Endpoints and Analyses

10.2.1. Primary Endpoint and Analysis

10.2.1.1. Primary Endpoint

The clinical benefit rate (CBR) is defined as the number and proportion of participants who are assessed with either a complete response (CR), a partial response (PR), or stable disease (SD) prior to 1 year after treatment start and show no evidence of loss of response nor progression

within that year. Response and progression will be assessed according to the Revised Response Evaluation Criteria in Solid Tumors (RECIST) v1.1.

10.2.1.2. **Primary Analysis Plan**

The primary analysis will be the calculation of the clinical benefit rate, (CBR), defined as the percentage of subjects in the analysis population who achieve a complete response (CR), partial response (PR), or stable disease (SD) as measured at 12 months \pm 1 month (approximately 1 year) from the start of treatment. CR, PR, and SD are as defined by RECIST v1.1. (See Appendix C RECIST v1.1). The CBR and the two-sided 95% Clopper-Pearson (exact) confidence interval will be calculated.

The analysis population will include all subjects who started nirogacestat and underwent cryoablation. Subjects who withdraw from the study prior to start of treatment or before receiving cryoablation and completing 1 year of treatment will be replaced.

10.2.1.3. **Relevant Subset for Primary Objective and Endpoint**

Evaluable subjects are those subjects who have received cryoablation therapy and completed 1 year of treatment.

10.2.1.4. **Primary Objective and Endpoint Assessment Methods**

CBR will be evaluated on the basis of clinical response as measured using imaging by MRI scan and evaluated by RECIST v1.1 (Appendix C). Determination of response will be made by the treating investigator.

10.2.1.5. **Measurement Time Points for Primary Objective / Outcome**

Imaging will be performed at screening, then every 3 cycles (ie, every 12 weeks \pm 14 days) until End of Treatment. MRI scan will be used at screening and at subsequent time points.

10.2.2. **Secondary Endpoints and Analysis**

10.2.2.1. **Clinical Benefit Rate (CBR) assessed by modified RECIST**

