For tumors with MRI enhancement, CBR will be evaluated on the basis of clinical response as measured using imaging by MRI scan and evaluated by modified RECIST (Appendix D). Determination of response will be made by the treating investigator. Imaging will be performed at screening, then every 3 cycles (ie, every 12 weeks \pm 14 days) until End of Treatment. MRI scan will be used at screening and at subsequent time points.

10.2.2.2. **Median Progression-free Survival (PFS)**

Median progression free survival (PFS) will be measured using imaging by MRI scan and evaluated by RECIST v1.1, mRECIST, and volumetrically (change in tumor volume as assessed by MRI volumetric).

Progression-free survival is defined as the time from start of treatment to date of progression or death due to any cause. If a subject is not known to have progressed or died, then PFS will be censored at the latest date the subject was known to be alive or progression-free (on or before the cut-off date). The PFS distribution will be estimated using the Kaplan-Meier method, and

the Kaplan-Meier curves, medians and 95% confidence intervals of the medians will be presented.

10.2.2.3. **Objective Response Rate (ORR) at 1 year**

For the objective response rate (ORR) at 1 year, the percentage of subjects who start study treatment and achieve an objective response (CR or PR) will be calculated. ORR will be measured using imaging by MRI scan and evaluated both RECIST v1.1, mRECIST, and MRI volumetric.

The ORR will be calculated as the proportion of subjects with objective response. The ORR and the two-sided 95% Clopper-Pearson (exact) confidence interval will be calculated.

10.2.2.4. **Time to Response (TTR)**

Time to response is defined as the time from the start of treatment with nirogacestat to the first objective tumor response (CR or PR), and will be measured using imaging by MRI scan and evaluated by RECIST v1.1, mRECIST, and volumetrically.

The TTR distribution will be estimated using the Kaplan-Meier method, and the Kaplan-Meier curves, medians and 95% confidence intervals of the medians will be presented.

10.2.2.5. **Duration of Response (DoR)**

Duration of response (DoR) is defined as the time from the date of documented disease response (CR or PR) to the date of the first documented progression, and will be determined using imaging by MRI scan and evaluated by RECIST v1.1, mRECIST, and volumetrically.

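### CBR is counted from the first nirogacestat dose, but its denominator admits only subjects who went on to cryoablation, so lead-in failures who are not ablated drop out of the primary rate

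*Protocol*

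**What the plan says.** The synopsis gives the primary endpoint as "Clinical benefit rate (CR + PR + SD) at 1 year from treatment start with nirogacestat". Section 10.2.1.1 requires a response or stable disease with no loss of response and no progression during that year.

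Sections 2.1.3 and 5.3 place cryoablation between Cycles 3 and 4, after a staging scan. Section 10.2.1.2 then defines who is analysed: "The analysis population will include all subjects who started nirogacestat and underwent cryoablation". It adds: "Subjects who withdraw from the study prior to start of treatment or before receiving cryoablation and completing 1 year of treatment will be replaced".

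The other analyses start from treatment. For objective response rate (ORR), section 10.2.2.3 says "the percentage of subjects who start study treatment and achieve an objective response (CR or PR) will be calculated". Section 10.2.2.2 times progression-free survival from the start of treatment, and section 10.2.2.6 tabulates safety for everyone who started.

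Section 3.7.2 says the investigator may stop treatment on progression. It also keeps a subject who has stopped under follow-up on the study schedule, if the subject allows it.

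**The concern.** The endpoint window opens about 12 weeks before the event that admits a subject to the denominator. Membership of the primary population is thus decided by something that happens after baseline and inside the outcome window.

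A subject with progression on the pre-cryoablation scan who is not ablated meets the definition of failure in 10.2.1.1 and is then removed by 10.2.1.2. No section of the protocol counts such a subject against the CBR.

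At stake is what the primary figure means. The strategy under test is lead-in, then cryoablation, then continued drug. The reported CBR would describe only those who reached the second step, yet section 10.4 sets it against a 1-year benchmark. CBR and ORR would also be reported on different denominators.

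**Working it through.** **Inputs**

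- Lead-in: 3 cycles × 28 days = 84 days = 12 weeks of the 52-week window (section 2.1.3).
- Enrolment: up to 23 for 20 evaluable (section 10.4.1), so at most 3 spare places; 3/23 = 13.0%.
- Test: null 0.5, alternative 0.8, one-sided exact, alpha 0.05 (section 10.4.2).
- Lead-in loss rate d: not given. Assumed range 0 to 13%.

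**Step 1. The plan's own figure.** Section 10.4.2 states 100.0% power with 20 subjects. The exact tail is P(X ≥ r) = Σ C(n,x) p^x (1−p)^(n−x), summed from x = r to n. With n = 20, r = 14 gives type I error 0.0577, which is too large. With r = 15 it is 0.0207 and power is 80.4%. The stated 100.0% is therefore not reproduced at alpha 0.05. It is approached only with the cut-off of 11 in section 10.4.4 (power 99.7%), whose type I error is 0.412. That is a separate matter. Below I use 15 of 20, the smallest cut-off that respects the stated alpha.

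**Step 2. Effect on a given result.** Let k subjects be lost in the lead-in, all non-benefit, with 20 cryoablated. As written, the denominator is 20; counting all starters, it is 20 + k.

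| k | 15 successes | exact p | 16 successes | exact p |
|---|---|---|---|---|
| 0 | 15/20 = 75.0% | 0.021 | 16/20 = 80.0% | 0.006 |
| 1 | 15/21 = 71.4% | 0.039 | 16/21 = 76.2% | 0.013 |
| 2 | 15/22 = 68.2% | 0.067 | 16/22 = 72.7% | 0.026 |
| 3 | 15/23 = 65.2% | 0.105 | 16/23 = 69.6% | 0.047 |

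At 15 successes, two lead-in failures are enough to reverse the conclusion. At 16, none of these cases reverses it.

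**Step 3. Effect on the error rate.** If the true CBR among all starters is 0.50 and a share d is lost with no benefit, the CBR among the cryoablated is 0.50/(1 − d).

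| d (assumed) | CBR among cryoablated | P(at least 15 of 20) |
|---|---|---|
| 0 | 0.500 | 2.1% |
| 5% | 0.526 | 3.5% |
| 10% | 0.556 | 6.1% |
| 13% (3/23) | 0.575 | 8.5% |

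**Step 4. How far this rests on losses being non-benefit.** If the lost subjects have benefit rate b and the cryoablated have rate q, the all-starter rate is (1 − d)q + db. The bias is q minus that, or d(q − b). With q = 0.75, d = 3/23 and b = 0, it is 0.1304 × 0.75 = 0.098, the gap between 75.0% and 65.2%. If one of the three lost subjects is still free of progression at 1 year, the figure is 16/23 = 69.6% (p = 0.047). The bias is upward whenever b is below q.

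**The case against.** The strongest reply is that few subjects may be lost. Section 1.2.4 reports no progressive disease in the phase 2 desmoid study and no objective progression among the evaluable desmoid subjects in phase 1. The 20% who stopped for adverse events in phase 3 (14 of 69) are not confined to the first 12 weeks. The three spare places must also cover losses after cryoablation. All of this stands, so the three-loss case is an upper illustration and not a forecast.

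The benchmark in section 10.4.3 consists of subtotally cryoablated tumours, which gives some reason to look at an ablated set. That supports a supportive analysis. It does not justify starting the clock 12 weeks before the event that admits a subject. Section 10.5 also reports lead-in response separately, and progression-free survival and safety run from treatment start. Lead-in failures thus leave the CBR but not the whole report.

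Four stronger readings are tempting but not supported:

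- *Every lead-in progressor disappears.* Section 3.7.2 makes stopping permissive. A progressor who is still ablated stays in the denominator as a failure.
- *Every loss is a failure under 10.2.1.1 and is replaced.* Stopping for toxicity is not itself a failure there, and the replacement sentence speaks of withdrawing from the study. Exclusion of the unablated follows from the population sentence alone.
- *Section 4.2 selects on the drug's own effect.* It says subjects are "limited to one cryoablation treatment session at time of intervention for desmoid tumors that can be at least 50% treated with cryoablation", and section 1.1 hopes the lead-in may "potentially lead to improved cryoablation success if there is tumor shrinkage". The time phrase most naturally belongs to the single session, as the parallel sentence in 1.1 shows. No section orders ablatability to be re-tested against the entry range. Losing tumours that shrink would, moreover, lower CBR.
- *Section 3.5.1 contradicts 10.2.1.2.* On the first-treatment date it says only "This date may be used as the cut-off criteria for which subjects will or will not be included in results reported to ClinicalTrials.gov". That is optional and concerns registry reporting.

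**Conclusion.** The mismatch between clock and denominator is real and can be read directly from sections 10.2.1.1 and 10.2.1.2. It would remain if the requirement in 10.2.1.3 to complete 1 year of treatment were removed. When the lost subjects do worse than those analysed, the CBR is biased upward.

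The size is uncertain. With up to 10% of starters lost as failures, the chance that a treatment at the null reaches 15 of 20 rises from 2.1% to at most 6.1%. A borderline result can change sides with two losses. These figures assume that lead-in losses are non-benefit, that 20 subjects are cryoablated and that the cut-off is valid at 0.05. The loss rate itself is an assumption.

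The population should be settled before outcome data are reviewed. In an open-label, single-arm trial with response judged by the treating investigator, a denominator chosen afterwards would carry little weight.

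**What to change.** In section 10.2.1.2:

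- Define the primary population as all subjects who received at least one dose of nirogacestat.
- Count progression or death before cryoablation as no clinical benefit.
- For subjects who stop the drug or miss cryoablation without progression, use the 1-year scan where follow-up continues under 3.7.2. Count those with no 1-year assessment as no benefit.
- Replace only subjects who withdraw before the first dose.
- Keep the cryoablated set as a supportive analysis, because it matches the benchmark in 10.4.3.

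Align section 10.2.1.3, the wording on 23 enrolled for 20 evaluable (synopsis, 2.1.3, 10.4.1) and section 10.4.4. The cut-off should be the exact one for the number who actually start:

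| N | cut-off | type I error | one fewer |
|---|---|---|---|
| 20 | 15 | 0.021 | 0.058 |
| 21 | 15 | 0.039 | 0.095 |
| 22 | 16 | 0.026 | 0.067 |
| 23 | 16 | 0.047 | 0.105 |

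The cost is wording in these sections and a CBR that may be less favourable. No new visits are needed, and the cryoablated-only figure can still be reported.

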3.5. Treatment Period and Duration

Treatment may continue via this study protocol for up to 24 months (26 cycles of treatment), unless there is progression of disease, intolerance, start of new anticancer therapy (as defined in Section 5.7.2.), or one of the criteria in Section 3.7 (Subject Study Completion or Termination) occurs. After 24 months of treatment, if clinically indicated, a subject may transition to commercial nirogacestat supply, once the subject has completed the End of Treatment (EOT) visit and is off study.

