3.7.2. Investigator-initiated Discontinuation of Study Treatment

The investigator may require a study subject to discontinue study treatment in the event of one of the following:

- The study subject has disease progression.
- Noncompliance
- The study subject needs treatment not allowed in the study.
- Pregnancy

- The study subject develops an AE that cannot be tolerated or that cannot be controlled with other medication.
- The investigator feels that it is in subject's best interest to stop treatment.
- The study subject is unable to meet study requirements.
- New information about the treatment of desmoid tumor becomes available.

If study therapy is stopped but the study subject allows the physician to submit follow up information, subject will continue to be followed clinically according to the study schedule.

If a subject must be removed from the study, the reason for the study removal and the date the subject was removed will be documented in the subject documentation/Case Report Form (CRF).

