3.8.1. Primary Completion

Primary completion is the date that the final datum is obtained/expected to be obtained for the primary outcome. This is primarily a concept for ClinicalTrials.gov results reporting. The timeframe for primary completion for an individual subject is approximately 12 months from start of treatment. Based on completion of the projected accrual of 20 evaluable subjects within 25 months (including the 28-day screening period), the last datum for the primary objective / outcome is expected to be obtained approximately 37 months from the time the study opens to accrual.

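### Protocol 10.2.1.3 and the replacement sentence in 10.2.1.2 require a completed year of treatment, which conflicts with the 10.2.1.2 analysis population and, if applied, drops early progressors from the primary denominator

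*Protocol*

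**What the plan says.** Section 10.2.1.1 makes progression within the year a failure: a subject with clinical benefit must "show no evidence of loss of response nor progression" in that year.

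Section 10.2.1.2 gives the CBR formula, "defined as the percentage of subjects in the analysis population who achieve a complete response" (or partial response or stable disease) at about 12 months. It then defines that population: "The analysis population will include all subjects who started nirogacestat and underwent cryoablation". No minimum treatment duration is attached. The next sentence provides for replacing subjects who withdraw before starting, or before having had cryoablation and a full year of treatment.

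Section 10.2.1.3, whose heading ties it to the primary objective and endpoint, says: "Evaluable subjects are those subjects who have received cryoablation therapy and completed 1 year of treatment".

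The recruitment target uses the 10.2.1.3 term: "Up to 23 enrolled subjects, to achieve 20 evaluable subjects" (Synopsis and section 2.1.3, and in similar words section 10.4.1). Section 3.8.1 also projects the accrual of 20 evaluable subjects.

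On stopping, section 3.5 lets treatment run for up to 24 months "unless there is progression of disease, intolerance" or another listed reason applies. Section 3.7.2 is permissive: "The investigator may require a study subject to discontinue study treatment in the event of one of the following", with disease progression first on the list. It adds that subjects off therapy who agree are still followed on the study schedule.

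**The concern.** One endpoint has two populations in adjacent subsections, and the difference between them depends on the outcome. Take a subject who has cryoablation, progresses at month 8 and stops. That subject is a failure under 10.2.1.1, is in the denominator under 10.2.1.2, and is not evaluable under 10.2.1.3. Nothing in the protocol ranks the two definitions or says that early progressors remain evaluable as failures.

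The replacement sentence points the same way. It speaks of withdrawal from the study, which is not the same as stopping treatment. Because it mentions the full year of treatment, though, it can be read as allowing a subject lost after cryoablation to be replaced.

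The trial is single-arm and open-label, and the treating investigator reads response (10.2.1.4). If the narrower definition were applied, the failures that the endpoint is meant to count would be removed and an inactive combination could look active.

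**Working it through.** **Inputs from the protocol.** Null CBR 0.5 and alternative 0.8 (10.4.2); 20 evaluable subjects from at most 23 enrolled (Synopsis, 2.1.3, 10.4.1); two-sided 95% Clopper-Pearson interval (10.2.1.2). The protocol gives no CBR for either population, so there is no figure of its own to reproduce on this point.

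**Assumption.** Let f be the share of failures who stop before one year and so drop out under 10.2.1.3. The protocol does not give f. It is shown from 0 to 100% because stopping at progression is usual under 3.5 but not mandatory under 3.7.2.

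**1. Expected reading.** With p the true CBR among cryoablated subjects, benefiters stay and a fraction 1 − f of failures stay:

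reading = p / [p + (1 − p)(1 − f)]

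For p = 0.5 and f = 0.5: 0.5 / (0.5 + 0.5 × 0.5) = 0.667.

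| f | true 50% reads as | true 80% reads as |
|---|---|---|
| 0% | 50% | 80% |
| 25% | 57% | 84% |
| 50% | 67% | 89% |
| 75% | 80% | 94% |
| 100% | 100% | 100% |

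At f = 75% a treatment at the null reads as the design alternative.

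**2. Effect on the planned interval, no replacement.** Take 20 cryoablated subjects at a true CBR of 50%. The number benefiting is x ~ Bin(20, 0.5), the number of failures removed is r ~ Bin(20 − x, f), and x/(20 − r) is analysed. The chance that the 95% Clopper-Pearson interval lies wholly above 50% is:

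| f | 0% | 25% | 50% | 75% | 100% |
|---|---|---|---|---|---|
| chance | 2.1% | 6.0% | 18.0% | 47.9% | 97.9% |

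As an illustration, 10 of 20 benefiting is 50% (CI 27 to 73%). With 5 failures removed it is 10/15 = 67% (38 to 88%); with 8 removed, 10/12 = 83% (52 to 98%).

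**3. What the enrolment cap allows.** If 20 evaluable subjects are reached, at most 23 − 20 = 3 subjects can have been removed. Suppose all 23 are cryoablated, 16 benefit, and 3 of the 7 failures stop early:

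- 10.2.1.2 population: 16/23 = 70% (47 to 87%)
- 10.2.1.3 subset: 16/20 = 80% (56 to 94%)

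The lower limit moves from below to above the 50% null.

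**4. How often 20 evaluable would be reached.** At a true CBR of 50% with all 23 cryoablated, removals follow Bin(23, 0.5f), and P(removals ≤ 3) is:

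| f | 25% | 50% | 75% | 100% |
|---|---|---|---|---|
| chance | 68% | 14% | 1.0% | 0.02% |

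With much removal, the likely result under the null is a shortfall of evaluable subjects, not a full set of 20 with an inflated rate.

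**The case against.** The strongest reply is that the protocol already fixes the denominator. The formula in 10.2.1.2 names the analysis population and defines it, and no section computes the CBR or its interval on evaluable subjects. Outside 10.2.1.3 that term serves as an accrual target, so 10.2.1.3 could be read as a rule for counting recruitment. This stands in part: it makes the harm conditional. It does not remove the conflict, because 10.2.1.3 is headed for the primary endpoint and the replacement sentence repeats its condition.

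A reader might infer that the primary analysis is planned on completers only, so that the CBR is certain to be inflated. The formula does not support that. A reader might also take 20 evaluable subjects as given and compute the chance of passing a cut-off such as 11/20 with half or more of the failures removed. The cap of 23 rarely allows 20 evaluable subjects there. The 11/20 rule in 10.4.4 also has a separate defect: at a true CBR of 50% it is met 41% of the time with nothing removed. Those probabilities are therefore not used.

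Finally, f is unknown and its upper end is extreme. Section 3.7.2 does not oblige a stop at progression, and it provides for follow-up off therapy, so outcomes need not be lost. That is why f starts at zero. It also means that these subjects can usually be classified and kept.

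**Conclusion.** The inconsistency is real and should be corrected before the primary data lock. It is two stated rules that cannot both hold, not a detail left to the analysis plan. Bias in the CBR follows only if 10.2.1.3 is taken as the denominator or early progressors are replaced; on the 10.2.1.2 population, with progressors kept, it does not arise.

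If the narrower rule is applied, the direction is upward for every progressor removed. The size depends on f, which has to be assumed. With a full 20 evaluable subjects inside the cap, the distortion is limited to three removed subjects, which can still be enough to carry the lower confidence limit across the null. The calculations cover failures only. The one-year condition would also remove subjects who stop for toxicity or by choice, and their effect on the CBR depends on their response status.

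**What to change.** Make three wording changes in section 10.2.1:

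1. In 10.2.1.3, delete the requirement of a completed year of treatment, so that evaluable subjects are the same as the 10.2.1.2 analysis population.
2. In the 10.2.1.2 replacement sentence, delete the reference to completing that year, so that only subjects lost before cryoablation are replaced.
3. State that subjects with progression, death or no one-year assessment after cryoablation stay in the denominator as non-benefit and are not replaced.

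The second change is needed as well as the first; otherwise the same condition would survive in the replacement rule. The target of 20 and the cap of 23 can stay as they are. No new data, visits or change in patient management are involved. The cost is an amendment to the text and a reported CBR that may be lower than under 10.2.1.3, in part because a missing one-year assessment counts against the treatment.
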